4.1. Overall Design

This is a phase 2b pivotal, multi-center, dose-finding study to evaluate the efficacy, safety, and immunogenicity of izokibep in subjects with moderate to severe HS.

This study consists of 2 parts, Part A and Part B as described below.

4.1.1. Part A: Single-arm, Open-label

Part A is a single-arm, open-label, proof-of-concept investigation to explore preliminary efficacy and safety of izokibep in adult subjects with moderate to severe HS. Part A consists of up to a 28-day screening period, a 31-week treatment period and a follow-up period that includes 2 visits to be completed by all subjects at Week 39 and Week 45. For subjects who early terminate, the follow-up visits should be completed 8 weeks (\pm 5 days) and 14 weeks (\pm 5 days) after the last dose of study drug. A minimum of 20 subjects and up to 30 subjects will be enrolled into Part A and treated with izokibep SC 160 mg QW (Group 0).

Subjects will complete study assessments according to the study visits outlined in the Schedule of Activities (SoA) (Section 1.3). The primary endpoint will be assessed at Week 16.

After enrollment and through the end of the study if the subject's AN count is $\geq 150\%$ of Day 1 AN count, antibiotic rescue medication is permitted (Section 6.8.3).

Once Part A is fully enrolled, subsequent subjects will be enrolled into Part B.

4.1.2. Part B: Randomized, Double-blind, Dose-finding

Part B is a randomized, double-blind, placebo-controlled, parallel-group, dose-finding investigation to evaluate the efficacy, safety, and immunogenicity of izokibep in subjects with moderate to severe HS. Subjects will complete up to a 28-day screening period, followed by a 16-week double-blind treatment period. At completion of the Week 16 visit procedures, subjects randomized to placebo will be switched to active treatment in a blinded manner for the Week 16 dose through Week 30 (Q2W dose group) or Week 31 (QW dose group). Subjects randomized to izokibep will remain on the same dose through Week 30 (Q2W dose group) or Week 31 (QW dose group). After their respective treatment periods, all subjects will enter a follow-up period that includes 2 visits to be completed at Week 39 and Week 45. For subjects who early terminate, the follow-up visits should be completed 8 weeks (± 5 days) and 14 weeks (± 5 days) after the last dose of study drug.

Approximately 170 subjects will be randomized into 1 of 4 groups in a 1:1:2:2 ratio as follows:

- Group 1 (n = 28-29): placebo SC QW from Day 1 (Week 0) to Week 15, then izokibep SC 160 mg QW from Week 16 to Week 31.
- Group 2 (n = 28-29): placebo SC Q2W from Day 1 (Week 0) to Week 14, then izokibep SC 160 mg Q2W from Week 16 to Week 30.
- Group 3 (n = 56-57): izokibep SC 160 mg QW from Day 1 (Week 0) to Week 31.
- Group 4 (n = 56-57): izokibep SC 160 mg Q2W from Day 1 (Week 0) to Week 30.

Randomization will be stratified by any prior biologic/Janus Kinase (JAK) inhibitor use for HS (Yes/No) and Hurley Stage (II or III).

Subjects will complete study assessments according to the study visits outlined in the SoA.

Subjects in the QW dosing groups (Group 0 [Part A], Groups 1 and 3 [Part B]) will have study visits at screening, Day 1 (Week 0), and at Weeks 1, 2, 3, 4, 8, 12, 13, 14, 15, 16, 17, 20, 24, 28, and 32 as well as at the follow-up visits.

Subjects in the Q2W dosing regimens (Groups 2 and 4 in Part B) will have study visits at screening, Day 1 (Week 0), and at Weeks 2, 4, 8, 12, 14, 16, 18, 20, 24, 28, and 32 as well as at the follow-up visits.

Subjects assigned to placebo SC QW and placebo SC Q2W will be grouped together into a single placebo group for comparison to each dosing regimen of izokibep for Part B. The primary endpoint will be assessed at Week 16.

After randomization and through the end of the study if the AN count is $\geq 150\%$ of Day 1 AN count, antibiotic rescue medication is permitted (Section 6.8.3).

4.1.3. Independent Data Monitoring Committee

An independent Data Monitoring Committee (DMC) will be established to monitor data on an ongoing basis to ensure the continuing safety of the subjects enrolled in this study.

The DMC will consist of at least one medical expert with the relevant therapeutic area expertise and at least one statistician. The DMC will also have a minimum of 3 members, one of whom will serve as the Chair. The DMC responsibilities, authorities, and procedure will be documented in the DMC charter. Over the course of the study the DMC will meet every 6 months to review interim data. After each review, the DMC will make recommendations regarding the continuation of the study based on safety. In addition, the DMC will meet as indicated below to review data from Part A and Part B.

Part A

The DMC will review data in Part A, after all subjects have had the opportunity to complete the Week 8 visit (or discontinued the study early). Based on this review, the DMC may recommend continuing, stopping, or altering Part B (Section 9.4).

Part B

In Part B, no formal interim analysis is planned for purposes of stopping or altering this study (Section 9.4). The DMC will review unblinded data when the first approximately 105 subjects randomized into Part B have had the opportunity to complete the Week 8 visit to make a recommendation on further development activities for izokibep. The DMC will not be empowered to recommend stopping this study or changing the sample size due to a demonstration of positive efficacy. The type I error rate for hypothesis tests at the end of the study will be decreased by 0.0001 to account for this interim summary of unblinded data. The study team and the investigators will remain blinded to these interim results until after the study is completed.

4.1.4. Number of Sites

Approximately 50 sites across North America and Europe will participate in this study. Additional sites and regions may be added. Sites that do not screen subjects within 2 months of site initiation may be closed.

4.1.5. Number of Subjects

Participants in this clinical investigation shall be referred to as "subjects." A minimum of 20 subjects and up to 30 subjects will be enrolled into Part A and approximately 170 subjects will be enrolled/randomized into Part B. Subjects who are withdrawn or removed from treatment, or the study will not be replaced.

4.1.6. Study Duration for Subjects

The maximum planned length of participation in the study for an individual subject is up to 49 weeks, which includes the following:

- Screening period of up to 28 days (4 weeks)
- 31-week treatment period
- Follow-up visit at Week 45

4.1.7. Scientific Rationale for Study Design

The design of this clinical trial was chosen to evaluate izokibep in subjects with moderate to severe HS. Part A is a proof-of-concept, single-arm, open-label part to generate preliminary data on the efficacy and safety of izokibep. The purpose of Part B (Weeks 0 to 16) is to provide 16-week placebo-controlled data demonstrating the safety and efficacy of izokibep administered SC at a dose of 160 mg QW and 160 mg Q2W for the treatment of HS. After Week 16, subjects randomized to izokibep will continue on the same blinded dosing regimen and subjects randomized to placebo will receive blinded active treatment (izokibep 160 mg QW or 160 mg Q2W) until Week 31. Long term safety and efficacy beyond Week 16 will be explored from Week 16 to Week 32 and will provide information on flares for subjects who achieved HiSCR on izokibep during the first 16 weeks of treatment.

Standard statistical procedures will be utilized in this study. Efficacy measurements in this study have been selected or designed to assess disease activity in subjects with moderate to severe HS. All clinical and laboratory procedures in this study are standard and generally accepted.

Males and females ≥ 18 years and ≤ 75 years with moderate to severe HS (AN count of ≥ 5) who meet all inclusion criteria and who do not meet any of the exclusion criteria are eligible for this study. The population being studied represents a population normally seen in clinical practice. This ensures the activity of izokibep can be evaluated across a distribution of disease severity in the study.

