ADAs = anti-drug antibodies; AN = abscess and inflammatory nodule; DLQI = Dermatology Life Quality Index; EQ-5D = European Quality of Life-5 Dimensions; HADS = Hospital Anxiety and Depression Scale; HiSCR = hidradenitis suppurativa clinical response; HS = hidradenitis suppurativa; IHS4 = International Hidradenitis Suppurativa Severity Score; NRS = numeric rating scale; PRO = patient-reported outcomes; SAE = Serious Adverse Event; TEAE = treatment-emergent adverse event.

Primary estimand

Please refer to Section 9.3.2.

Secondary estimand(s)

Please refer to Section 9.3.3.

¹ HiSCR50/75/90/100 is defined as at least a 50%, 75%, 90%, or 100% reduction from baseline in the total abscess and inflammatory nodule count, with no increase from baseline in abscess or draining fistula count.

² Flare is defined as \geq 25% increase in AN count with a minimum increase of 2 AN relative to baseline.

4. Study Design

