8.1.1.1. Hidradenitis Suppurativa Clinical Response

The HiSCR was developed to address issues with available HS scoring systems and is a validated measure that is responsive to improvement in disease activity, simplifies the scoring process, and increases the sensitivity to detect HS-specific lesions (Kimball et al, 2014; Kimball et al, 2016b). The HiSCR is defined as at least a 50% reduction from baseline in the total AN count, with no increase from baseline in abscess or draining fistula count. HiSCR50, HiSCR75, HiSCR90, and HiSCR100 are defined as at least 50%, 75%, 90%, or 100% reduction respectively from baseline in the total AN count, with no increase from baseline in abscess or draining fistula count.

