9.3. Statistical Analyses

9.3.1. General Considerations

Data from Part A and Part B will be summarized separately.

All data collected will be summarized by planned timepoint without imputation. Continuous data will be summarized with count, mean, median, standard deviation, minimum, and maximum. Change from baseline will additionally include standard error. Categorical data will be summarized with count and percent. Time to event data will be summarized with product-limit estimators of median and quartiles. Placebo subjects assigned to receive doses QW or Q2W will be summarized both separately and combined, with hypotheses tested using both placebo dosing frequencies combined.

All hypothesis tests will use only data from Part B and will be reported with two-sided p-values. Comparison of QW dosing to placebo will use only subjects assigned to receive izokibep QW or

placebo; comparison of Q2W dosing to placebo will use only subjects assigned to receive izokibep Q2W or placebo. All CIs will be two-sided with nominal 95% coverage.

Data will be summarized by part and planned timepoint, using data collected at the visit. Study day will be calculated as post-baseline date minus randomization date, plus 1 (except that study day for pre-randomization dates will not include the plus 1). Day range windows will not be applied for summaries (but may be applied for protocol deviations). Baseline values will be the last value collected before randomization and change from baseline will be calculated as post-baseline value minus baseline value.

For testing purposes, subjects randomly assigned to placebo QW and placebo Q2W will be grouped together into a single placebo group for comparison to each dosing regimen of izokibep. This assumes that dosing with placebo QW or Q2W does not affect efficacy, an assumption which will be explored with simple summary statistics. Stratified tests will use the 4 strata from the randomization process. If a subject is incorrectly classified during the randomization process, the analysis will use the correct classification, not the classification used during randomization.

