2.4. Primary Efficacy Variable

The primary efficacy variable for Part A and Part B is HiSCR75, the proportion of subjects who achieve at least a 75% reduction from baseline in the total AN count, with no increase from baseline in abscess or draining fistula count. The primary timepoint for analysis is Week 12 for Part A and Week 16 for Part B.

HiSCR50/75/90/100 is defined as meeting all three criteria below:

- (AN count at baseline AN count at current visit) / AN count at baseline \times 100% \geq 50/75/90/100%
- Abscess count at baseline \geq abscess count at the current visit
- Draining fistula count at baseline \geq draining fistula count at the current visit

where AN count is abscess count + inflammatory nodule count, and abscess count and fistula count are summed across all regions and are inclusive of all abscesses, inflammatory nodules and fistula that have previously undergone localized surgical or medical intervention and are no longer present. The baseline value for lesion count (including draining fistula count) and Hurley stage is the latest value on or before the randomization day (Day 1).

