6.6.5. Exploratory Analysis

Exploratory endpoints will be analyzed analogously to primary and secondary endpoints with the same strategies for ICEs. Binary endpoints will be analyzed with a stratified test of risk difference and continuous endpoints will be analyzed with an MMRM model in general. Continuous data at timepoints before and including the primary timepoint will use all data from planned assessments up to and including the primary timepoint; continuous data after the primary timepoint will use all data from all planned assessments. Visit week, treatment group and interaction will be included in the MMRM model.

The number and proportion of subjects for binary endpoints in each treatment group will be reported, along with p-values, 95% CI without strata calculated using asymptotic Wald method will be reported as well. Results for continuous endpoints will presented as LS mean changes and associated SEs with associated 95% CI and p-values. For binary endpoints, a line plot showing the proportion of subjects experiencing such endpoints will be produced. For continuous endpoints, a line plot showing the LS mean and SE for each treatment group will be produced. Exploratory endpoint results will also be listed.

The following binary endpoints before or on Week 16 will be analyzed analogously to the primary endpoints of HiSCR75 at Week 16. The number and proportion of subjects for binary endpoints in each treatment group, p-values, 95% CI without strata calculated using asymptotic Wald method will be reported as well. The binary endpoints after week 16 will include number and proportion along with Clopper-Pearson 95% CI without strata according to the four randomized treatment groups. No p-value will be reported.

- HiSCR50, HiSCR75, HiSCR90 and HiSCR100 at Weeks 2, 4, 8, 12, 24 and 32;
- AN count of 0, 1, or 2 at Weeks 4, 8, 12, 24, and 32 among subjects with baseline Hurley Stage II;

- HS flares through Weeks 4 and 32;
- IHS4-55 response rates at Weeks 4, 8, 12, 16, 24 and 32;
- Draining fistula count of 0 at weeks 4, 8, 12, 16, 24 and 32
- Draining fistula count of 0 at weeks 4, 8, 12, 16, 24 and 32, among subjects with baseline draining fistula count of at least 1
- Draining fistula count of 0 at weeks 4, 8, 12, 16, 24 and 32, among subjects with baseline draining fistula count of at least 2

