 - First achievement of HiSCR90
 - First achievement of HiSCR50

- First achievement of AN count of 0, 1, or 2 for subjects with baseline Hurley Score II
- First achievement of ≥ 3 point reduction in NRS in Patient Global Assessment of Skin Pain at its worst among subjects with baseline NRS ≥ 4
 - To maintain consistency between all visits, only the score collected on the visit day will be used for this analysis.

These graphics will address the question of whether subjects originally randomized to placebo catch up in efficacy to the subjects who were randomized to izokibep by week 32.

The following analyses will be done by all four randomized treatment groups for the FAS subjects who had at least one dose of izokibep on or after Week 16. The analyses in subjects who received izokibep for the first 16 weeks will be done to address the question of whether responders/non-responders in the first 16 weeks of treatment experience subsequent sustained or added benefit in the following 16 weeks of treatment. The analyses in subjects who received placebo for the first 16 weeks will be done to evaluate if there is additional benefit after initial placebo response, or if placebo non-responders catch up to the subjects receiving 32 weeks of izokibep.

- The subgroup of subjects who were responders by HiSCR75 at Week 16 will be further evaluated by randomized treatment group at Week 24 and Week 32:
 - Response rate for HiSCR75, HiSCR100, HiSCR90, HiSCR50 will be summarized by randomized treatment group at Week 24 and Week 32. The responder proportions and Clopper-Pearson 95% CI without strata will be presented. The NRI approach to missing data will be the same as for the primary analysis.
 - Response rate for AN count of 0, 1, or 2 among those with Hurley stage II at baseline will be summarized by randomized treatment group at Week 24 and Week 32. The responder proportions and Clopper-Pearson 95% CI without strata will be presented. NRI approach will be the same as for the primary analysis.

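### Weeks 16–32 are meant to inform on flares in izokibep responders, but no planned analysis reports them, and the Day 1-based flare rule misses a responder's full return to the entry count

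*Protocol*

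**What the plan says.** Protocol 4.1.7 describes Weeks 16 to 32 as exploring longer-term safety and efficacy, and adds that this period "will provide information on flares for subjects who achieved HiSCR on izokibep during the first 16 weeks of treatment".

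Flare is defined in Protocol Section 3 (second footnote to the objectives table) as at least a "25% increase in AN count with a minimum increase of 2 AN relative to baseline". Protocol 9.3.1 fixes the reference: "Baseline values will be the last value collected before randomization". SAP 2.4 likewise ties the lesion-count baseline to Day 1. Neither resets it at Week 16 for subjects randomised to izokibep.

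HiSCR without a suffix is defined in Protocol 8.1.1.1 as "at least a 50% reduction from baseline in the total AN count, with no increase from baseline in abscess or draining fistula count".

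Three parts of the SAP bear on flare or relapse after Week 16:

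- SAP 6.6.5 lists "HS flares through Weeks 4 and 32" as an exploratory binary endpoint, by randomised group.
- SAP 6.6.7 follows Week 16 responders to ask "whether responders/non-responders in the first 16 weeks of treatment experience subsequent sustained or added benefit". It lists HiSCR50/75/90/100 and AN count 0–2 at Weeks 24 and 32, mixed models for IHS4 and draining fistula count, and McNemar tests of Week 16 against Week 32 response. Flare is not on the list.
- SAP 6.6.7 also defines a flare from Week 16 to Week 32, but only for placebo-randomised subjects who took izokibep in Period 2, still had an AN count of at least 5 at Week 16, and had lesions in at least two areas.

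**The concern.** The protocol names a product of the second treatment period that the SAP does not deliver. The flare result that is planned for izokibep subjects after Week 16 is also insensitive to relapse in the subjects of interest. A responder has, by definition, a count well below Day 1, and a flare is recorded only once the count has climbed back past Day 1 by a further 25%.

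The planned result is also cumulative. A responder who flared at Week 4 and then improved is counted in the Week 32 figure. In Groups 1 and 2, flares on placebo are pooled with flares after the switch to izokibep.

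At stake is the reading of the flare result as evidence on whether response holds, in a study described as pivotal. The confirmatory testing is not involved.

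**Working it through.** The plan gives no figure on this point to reproduce. The check applies its definitions to lesion counts.

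**Inputs.** Day 1 AN count *b* ≥ 5 (Protocol 5.1, criterion 5); flare = rise of at least 25% and at least 2 lesions (Protocol Section 3); HiSCR50 and HiSCR75 = fall of at least 50% or 75% (Protocol 8.1.1.1). Only the AN part of HiSCR enters the arithmetic.

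**Formulas.**

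- Day 1-referenced flare starts at max(⌈1.25*b*⌉, *b* + 2).
- Highest Week 16 count *r* that qualifies: ⌊0.25*b*⌋ for HiSCR75, ⌊0.5*b*⌋ for HiSCR50.
- Week 16-referenced flare starts at max(⌈1.25*r*⌉, *r* + 2).

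| Day 1 AN | Day 1 flare starts at | Largest count not a flare | HiSCR75: highest Week 16 count → Week 16 flare starts at | HiSCR50: same |
|---|---|---|---|---|
| 5 | 7 | 6 | 1 → 3 | 2 → 4 |
| 10 | 13 | 12 | 2 → 4 | 5 → 7 |
| 20 | 25 | 24 | 5 → 7 | 10 → 13 |
| 40 | 50 | 49 | 10 → 13 | 20 → 25 |

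From the highest qualifying Week 16 count, a HiSCR75 responder can therefore rise by 500%, 500%, 380% and 390% in these four rows without a flare; for example (24 − 5)/5 = 380%. A HiSCR50 responder can rise by 200%, 140%, 140% and 145%. In each case the final count exceeds Day 1.

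**Full return to Day 1.** Against Day 1 the rise is zero, so it is never a flare. Against Week 16, *r* ≤ *b*/2 gives a rise of at least 100% and, with *b* ≥ 5, of at least 3 lesions, so it is always a flare. Enumerating integer Day 1 counts from 5 to 60 (the upper limit is an assumption) with every AN-qualifying HiSCR50 count at Week 16 gives 0 of 952 pairs flagged with the Day 1 reference and 952 of 952 with the Week 16 reference.

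**Mixed reference in the placebo-switcher flare.** SAP 6.6.7 takes the percentage criterion from Week 16 but the 2-lesion criterion from baseline. With Day 1 = 20 and Week 16 = 10, the first is met from 13 (1.25 × 10 = 12.5) and the second only from 22. Counts of 13 to 21 are not flares, although 21 is a 110% rise from Week 16.

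**What the responder analyses cover.** A HiSCR75 responder who is back at the Day 1 count at Week 24 or 32 is a HiSCR non-responder there and is seen. Two things are not covered:

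- A relapse seen only at Week 28 or at an unscheduled visit. The Schedule of Activities has lesion counts at Weeks 24, 28 and 32, and its lesion-count footnote and Protocol 8.1.1 add counts at worsening or flare.
- HiSCR50-only responders, who fall in the HiSCR75 non-responder subgroup. The AN 0–2 subgroup picks up only those with Hurley Stage II, Day 1 counts of 5 to 7 and 2 lesions at Week 16, because 2 lesions from 8 is already a 75% fall.

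Non-response imputation in these analyses also mixes missing visits and antibiotic use with true relapse.

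**The case against.** Flare (worse than at entry) and loss of response (no longer HiSCR) are different concepts, and the SAP measures both. A single Day 1 reference keeps Weeks 4, 16 and 32 comparable. The protocol's objectives table promises only flares through Weeks 4 and 32, which the SAP delivers; 4.1.7 is rationale text. SAP 6.6 says that Part B efficacy is summarised by period, and flare through Week 16 is already a secondary endpoint. A Week 16 reference has its own weakness: selecting subjects for a low count and using that count as the reference invites regression to the mean, with no placebo arm after Week 16.

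Much of this stands. The Day 1 definition is legitimate and should stay. What does not follow is that 4.1.7 is met: no table gives flares in izokibep responders, and the general statement on periods does not define a Period 2 flare for them.

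Stronger readings are tempting and are not supported. A reader might infer that the question cannot be answered; the counts needed are collected. A reader might infer that flare rates after Week 16 will be close to zero and durability overstated; the documents give no distribution of relapse, worsening to 125% of Day 1 still counts, and the HiSCR rates and McNemar tests show loss of response. A reader might infer that Day 1 is the reference everywhere; the placebo-switcher analysis is a partial exception.

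**Conclusion.** The gap is real but limited. A purpose stated in Protocol 4.1.7 has no matching analysis, and the flare measure that covers izokibep subjects after Week 16 lets a responder return to the Day 1 count, or to just under 125% of it, without counting. Loss of response is covered indirectly at Weeks 24 and 32.

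The arithmetic shows what the rule can miss, not how often it will; the number of subjects affected cannot be estimated from the documents. The conclusion reads HiSCR in 4.1.7 as defined in Protocol 8.1.1.1 and takes response at Week 16, as SAP 6.6.7 does. If HiSCR75 was meant, the missing flare table remains and only the point about HiSCR50-only responders falls away.

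The analysis is exploratory. The primary endpoint, alpha and power are untouched. The change is worth making because it is cheap and lets the trial address a purpose it states.

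**What to change.** In SAP 6.6.7:

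- For izokibep-randomised subjects who met HiSCR50 at Week 16 and, separately, HiSCR75, add a descriptive proportion with at least one flare after Week 16 through Week 32. Measure both criteria (at least 25% and at least 2 lesions) from the Week 16 count; if that count is 0, apply only the 2-lesion criterion. Use the scheduled Week 24, 28 and 32 counts and any unscheduled counts.
- Show the Day 1-referenced rate for the same subjects beside it. A rise from 0 to 2 would count as a flare under the Week 16 reference, and regression to the mean will push that rate up.
- In the placebo-switcher flare, change the second criterion from baseline to the Week 16 count.

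In SAP 6.6.5, reconcile the cumulative flare through Week 32 with the period-wise summaries in SAP 6.6 by reporting Period 2 flares separately for the four randomised groups.

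The cost is SAP wording and one or two descriptive tables, with no new data and no effect on the testing sequence.
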